13. STATISTICAL ANALYSES

13.1. Study Patients

Patients will be advised in the Informed Consent Forms that they have the right to withdraw from the study at any time without prejudice, and may be withdrawn at the Investigator's / Sponsor's discretion at any time. In the event that a patient drops out of the study or is withdrawn, the withdrawal / study termination page in the CRF should be completed. On the withdrawal page the Investigator should record the date of the withdrawal, the person who initiated withdrawal and the reason for withdrawal. Reasonable effort should be made to contact any patient lost to follow up during the course of the study in order to complete assessments and retrieve any outstanding data and study supplies.

Withdrawn by the Investigator due to

- Serious Adverse Drug Reaction
- Lack of efficacy
- Consent withdrawn
- Administrative reasons

The patient or his/her representative requested withdrawal due to

Cerebrolysin and repetitive Transcranial Magnetic Stimulation (rTMS) in patients with Traumatic Brain Injury

- An Adverse Event for which the Investigator did not consider removal from the study.
- Perceived insufficient therapeutic effect.
- Withdrawal of consent for any other reason (data recorded until withdrawal will be kept in the database if not explicitly denied by the patient).

13.2. Demographic and Other Baseline Characteristics

Patients' demographics will be obtained at Screening (study day 30), alongside medical history, neurological and physical examinations and hematology and blood chemistry will be obtained.

Females who are pregnant or lactating will be excluded from the study. However, females of child bearing potential taking acceptable contraceptive precautions can be included. A highly effective method of birth control and one which is acceptable for this study, is defined as those which result in a low failure rate (i.e. less than 1% per year) when used consistently and correctly such as implants, injectables, combined oral contraceptives, some IUDs, sexual abstinence or vasectomised partner.

Some concomitant medication will exclude the patient from the study: steroids, Ca2+-channel blockers or major anticoagulants (e.g., warfarin and other coumarin derivates), monoamine oxidase inhibitors, antipsychotic drugs or nootropic molecules. All other concomitant medications and therapies will be recorded in the CRF.

13.3. Treatment Compliance

Each patient will receive three cycles of treatment of 10 infusions on 10 consecutive days:

- Study days 31-40,
- Study days 61-70
- Study days 91-100

Patients with compliance for the entire study below 80% for the treatments will be considered protocol violators and will not be included in the per protocol analysis.

Study Title

13.4. ANALYSIS OF EFFICACY

Descriptive statistics and graphs will be generated for the ITT population. In addition, nonparametric effect sizes and confidence intervals (Kruskal Wallis and Dunn's pot hoc test) will be provided for all primary and secondary efficacy criteria at all points in time.

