13.7. Level of Significance

The multiple level alpha is set to α = 0.05, one-sided, according to current recommendations for randomized phase II trials (Rubinstein 2009; Sumithra 2010; Manish 2011).

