According to the ICH Guideline E9 (ICH Topic E9, Statistical Principles for Clinical Trials, Step 4, Consensus guideline, 5 February 1998, CPMP/ICH/363/96) the results will be given as P-values as well as effect size measures with their confidence intervals (Mann-Whitney statistic as corresponding effects size measure of the Wilcoxon-Mann-Whitney test), so that the direction and quantity of the treatment effects are determined with their precision. The Mann-Whitney statistic is the most valuable effects size measure for the Wilcoxon-Mann-Whitney test because it is appropriate where the Hodges-Lehmann shift parameter is no longer valid. Furthermore, the Mann-Whitney effects size measure is appropriate for continuous, ordinal and binary data at the same time and represents an ideal effects size measure for multiple outcomes. Incidentally, the 25th Anniversary of the journal Statistics in Medicine dedicated a whole issue to papers about the Mann-Whitney statistic (D'Agostino, 2006).

The Mann-Whitney effects size measure (MW) gives the probability that a randomly chosen patient of the test group is better off than a randomly chosen patient of the comparison group, defined in statistical shortcut: P(X < Y) + 0.5 P(X = Y).

Applying the Mann-Whitney effects size measure, the null and alternative hypothesis for the comparisons of the test treatment to control treatment (superiority) can be formulated as follows:

 $\begin{array}{lll} H_0: & MW_{TC} \leq 0.50 \\ \\ H_A: & MW_{TC} > 0.50 \\ \\ H_0: \mbox{ Null-hypothesis; } H_A: \mbox{ Alternative Hypothesis; } T: \mbox{ Test Treatment; } \\ C: \mbox{ Control} \end{array}$

Protocol #: FSNN040418, v1.0 (final) Date: 040418 STUDY ID: CAPTAIN - rTMS

The traditional benchmarks for the Mann-Whitney effects size measure (MW) are as follows (Colditz, 1988):

- 0.29 large inferiority
 0.36 medium inferiority
 0.44 small inferiority
 0.50 equality
 0.56 small superiority
 0.64 medium superiority
- 0.71 large superiority

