13.11. Exploratory Analyses

All primary and secondary efficacy criteria will be analyze with descriptive group statistics.

In addition, nonparametric effect sizes and confidence intervals (Mann-Whitney effects size measure) will be provided for all primary and secondary efficacy criteria at all points in time.

Analysis procedures for Eye tracking parameters and Quantitative EEG parameters will be described in the Statistical Analysis Plan.

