13.14. Homogeneity Analyses (Exploratory Interpretation)

Homogeneity analyses for baseline shall be performed based on the ITT population.

In addition to descriptive analyses robust nonparametric Mann-Whitney effects size measures and their two-sided 95% confidence intervals shall present an overview on demographic-anamnestic variables and on the primary efficacy criteria at baseline. This allows comparison of baseline variables across different scales and data types.

As benchmark for relevant baseline differences, a Mann-Whitney effects size measure of 0.36 and 0.64 respectively will be applied (referring to a standardized difference of 0.5 according to Cohen, which is regarded as a medium-sized difference).

In the case of heterogeneities, stratified analyses will be performed as second line analyses.

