12.2 Confirmatory Statistics

Although this study is intended to be of exploratory nature, the analysis will be based on 'confirmatory' principles with pre-specification of the primary analyses and control of multiple level alpha.

Mean, median and distribution group difference hypotheses

• Kruskal-Wallis with Dunn's test.

Kruskal-Wallis Rank Sum Test will be used to assess the statistical significance of the differences across groups. The pairwise comparisons will be performed using Dunn's Kruskal-Wallis Multiple Comparisons, with the Bonferroni adjustment.

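### SAP 13.4 takes effect sizes and intervals from Kruskal-Wallis and Dunn's tests, which do not give the Mann-Whitney effect the protocol promises; no level is set for efficacy intervals

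*SAP*

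**What the plan says.** Protocol 13.10 states the hypotheses as a Mann-Whitney value (MW) against 0.50 and says that "the results will be given as P-values as well as effect size measures with their confidence intervals", naming the Mann-Whitney statistic as the measure. Protocol 13.11 adds that "nonparametric effect sizes and confidence intervals (Mann-Whitney effects size measure) will be provided for all primary and secondary efficacy criteria at all points in time".

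SAP 13.4 carries the second sentence over with a different parenthesis: "nonparametric effect sizes and confidence intervals (Kruskal Wallis and Dunn's pot hoc test) will be provided". The SAP section on confirmatory statistics (one of two numbered 12.2) specifies a Kruskal-Wallis test and then "Dunn's Kruskal-Wallis Multiple Comparisons, with the Bonferroni adjustment". The SAP does not mention the Mann-Whitney statistic anywhere, and 13.4 is its only reference to confidence intervals.

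On levels, protocol 13.7 says "The multiple level alpha is set to α = 0.05, one-sided". Neither document gives a confidence level for an efficacy interval. The SAP does not restate alpha or sidedness.

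**The concern.** The sentence in SAP 13.4 promises estimates but names two tests. An analyst who follows it has p-values and no defined effect measure for CRB + rTMS against CRB + sham, which is the primary question. The protocol expresses its hypotheses, its benchmarks for small, medium and large effects, and its design alternative (MW = 0.64) on the Mann-Whitney scale. If the SAP's output is not on that scale, the observed effect cannot be judged against any of them. For a phase II trial that calls itself exploratory, the estimate and its precision are arguably the main product.

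The missing level is a smaller gap of the same kind. Someone will have to choose it, and it should be chosen before unblinding.

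**Working it through.** **1. The plan's own scale.** Inputs from protocol 13.9: one-sided alpha 0.05, power 80%, MW = 0.64, correlation 0.4, 10% allowance, 30 per group. The Noether formula for one outcome is n = (1.645 + 0.842)² / (6 × 0.14²) = 6.183 / 0.1176 = 52.6 per group. Averaging K outcomes multiplies this by (1 + (K − 1) × 0.4)/K. For the nine listed scales the factor is 4.2/9 = 0.467, so n = 24.5, rounded up to 25, and 25/0.9 gives 28 against the stated 30. The K used by the plan is not stated: K = 6 gives 30 and K = 18 (nine scales at two times) gives 26. Two-sided 0.05 gives 36 for nine scales. The stated 30 therefore fits a one-sided 0.05 test of an effect expressed as MW.

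**2. What the two tests return.** Kruskal-Wallis returns one non-directional statistic for three arms. It contains no contrast. Dunn's test takes the difference in mean ranks, with ranks assigned over all three arms, and divides it by a standard error.

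**3. Why Dunn's difference is not the two-arm effect.** Call the arms A (CRB + rTMS), B (CRB + sham) and C (placebo + sham), with n per arm and ties counted half. The mean pooled rank of A is (n + 1)/2 + n × MW(A,B) + n × MW(A,C), and similarly for B. Subtracting,

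mean rank A − mean rank B = n × [2 × MW(A,B) − 1] + n × [MW(A,C) − MW(B,C)].

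The first term is the primary contrast. The second depends on the placebo arm and has no place in it.

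**4. Numerical check.** One simulated data set has 30 per arm. Arms A and B are held fixed with MW(A,B) = 0.688, and only arm C is shifted. Dunn's standard error is √(90 × 91/12 × 2/30) = 6.745. The Bonferroni column assumes three pairs and two-sided p, because the SAP gives neither.

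| Shift of placebo arm (SD) | Mean-rank difference A − B | Dunn z | Bonferroni p |
|---|---|---|---|
| −3 | 11.17 | 1.66 | 0.29 |
| −1 | 14.53 | 2.16 | 0.094 |
| 0 | 17.77 | 2.63 | 0.025 |
| +1 | 14.83 | 2.20 | 0.084 |
| +3 | 11.10 | 1.65 | 0.30 |

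The identity in step 3 explains the table. Its first term is 30 × (2 × 0.6878 − 1) = 11.27 in every row. The remainder, 17.77 − 11.27 = 6.50 in the middle row, comes from the placebo arm. The Mann-Whitney value for the primary contrast is 0.688 throughout.

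**5. The interval level.** The interval that agrees with a one-sided 0.05 test has a one-sided 95% lower limit, which is the lower end of a two-sided 90% interval. With nine components and 27 evaluable per arm (30 less 10%), the null-variance standard error is √(0.467 × 54/(12 × 27²)) = 0.054. Take an observed MW of 0.597, which is 1.8 standard errors above 0.50, with one-sided p = 0.036. The 90% interval is 0.508 to 0.685 and the 95% interval is 0.491 to 0.702. The level therefore decides whether the reported interval agrees with the test.

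**The case against.** The best defence is that nothing withdraws protocol 13.10. The confirmatory Mann-Whitney estimate is still promised there, and SAP 13.4 parallels only the exploratory sentence of protocol 13.11. SAP 8.2.1 and 9 still refer to a multivariate directional test, and the SAP's descriptive statistics include means with standard errors for raw and change values. This part stands: it would be too strong to say that the trial could report no estimate or precision at all. It does not rescue 13.4, because a difference in means is not the promised measure and the SAP nowhere computes that measure.

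It can also be said that an effect size could be derived from the tests, such as an omnibus epsilon-squared or z/√N. The SAP names neither. The first is not for the contrast, and the second inherits the dependence on the placebo arm shown above.

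A third objection is that 13.4 merely echoes the change of test in SAP 12.2. That is largely true, and the two should be revised together. But an amended test in 12.2 would leave the wrong parenthesis in 13.4.

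A reader might infer more: that the plan sets a two-sided 95% interval in conflict with its one-sided 0.05 test. The documents do not support this. Protocol 13.14 asks for "robust nonparametric Mann-Whitney effects size measures and their two-sided 95% confidence intervals" only in the exploratory baseline overview, which need not match the efficacy test, and no section applies that level to efficacy. If an analyst did carry it over, the chance at MW = 0.64 of a significant test with a 95% interval covering 0.50 would be about 8.0% to 9.1% for nine components (power 83.2% less 74.2% at 27 per arm, 86.5% less 78.5% at 30). It would be about 7.2% to 8.3% for 18. Those figures measure a hypothetical choice and are not the size of a defect in the plan.

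**Conclusion.** The point holds as a defect of estimation. As written, SAP 13.4 replaces the protocol's effect measure with two tests that do not produce it, for every primary and secondary efficacy criterion at every time point. The primary contrast is left without a specified estimate to compare with 0.64. This rests on the wording of the two documents and on the algebra in step 3, which holds for equal arm sizes. The simulated data set is an illustration only, and its Bonferroni column rests on an assumed number of pairs and sidedness.

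The secondary point is an omission: no level is stated for efficacy intervals. Recommending 90% assumes that the one-sided 0.05 Wei-Lachin test remains the primary test. The numbers in step 5 also assume nine components, a common correlation of 0.4 and the null variance.

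**What to change.** In SAP 13.4, replace the parenthesis naming the two tests with the Mann-Whitney effect size and its confidence interval, computed pairwise from the two arms concerned:

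- CRB + rTMS against CRB + sham (primary contrast);
- CRB + sham against placebo + sham (assay sensitivity);
- in addition, the pooled Wei-Lachin Mann-Whitney estimate for the primary ensemble.

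Orient each scale so that a value above 0.50 means the first-named arm is better off, in line with the definition in protocol 13.10.

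Settle the primary test in SAP 12.2 first, then state the level. If the protocol's one-sided 0.05 Wei-Lachin test stands, report the pooled primary estimate with a two-sided 90% interval, or a one-sided 95% lower bound, using the variance from the test. Label any 95% interval as descriptive. If the Bonferroni-adjusted Dunn test were kept instead, a 90% interval would not match it, and the SAP would have to state that test's alpha, sidedness and number of comparisons before a level could be chosen. The baseline intervals in protocol 13.14 can stay as they are.

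The cost is wording, with one line on the level in protocol 13.10 and SAP 13.4. The pooled estimate and its variance already come out of the Wei-Lachin calculation, and the pairwise values need no extra data.

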13.5. Secondary Objectives

To assess the single efficacy criteria at 3 and 6 months post TBI.

To test ET and qEEG parameters as biomarkers of cognitive dysfunction at 3 and 6 months post TBI.

To test ET and qEEG as treatment monitoring tools at 3 and 6 months post TBI.

To check assay sensitivity for the primary objective (rTMS + CRB versus CRB alone) by comparing CRB alone versus PLC.

To assess the safety of rTMS administrated starting with one month after TBI.

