5.2. Secondary Objectives

- To assess the single efficacy criteria at three and six months post TBI.
- To test ET and qEEG parameters as biomarkers of cognitive dysfunction.
- To assess the safety of rTMS administrated starting with one month after TBI.
- To check assay sensitivity for the primary objective (rTMS + CRB versus CRB alone) by comparing CRB alone versus PLC.

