8.2. Secondary Endpoints

- Eye tracking parameters
- Quantitative EEG parameters
- rTMS adverse events

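### The SAP's only inferential method that can reach eye tracking and qEEG is a between-arm rank test, which leaves the biomarker objective unanswered

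*SAP*

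**What the plan says.** The SAP (section 5.2) lists as a secondary objective "To test ET and qEEG parameters as biomarkers of cognitive dysfunction". Protocol section 4.2 has the same objective, and protocol section 13.5 adds the time points: "To test ET and qEEG parameters as biomarkers of cognitive dysfunction at 3 and 6 months post TBI". Section 13.5 also has an objective that appears in neither protocol section 4.2 nor SAP section 5.2: "To test ET and qEEG as treatment monitoring tools at 3 and 6 months post TBI".

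On method, protocol section 13.11 states: "Analysis procedures for Eye tracking parameters and Quantitative EEG parameters will be described in the Statistical Analysis Plan".

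The SAP (section 8.2) lists "Eye tracking parameters" and the qEEG equivalent as secondary endpoints, with no individual parameter named. Three later statements bear on how they would be analysed:

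- Section 12.2 on descriptive statistics lists one-variable summaries for all variables: range, extremes, mean, spread, skewness and kurtosis.
- Section 12.2 on confirmatory statistics says: "Kruskal-Wallis Rank Sum Test will be used to assess the statistical significance of the differences across groups". Pairwise comparisons follow by Dunn's test with Bonferroni adjustment.
- Section 13.4 says: "nonparametric effect sizes and confidence intervals (Kruskal Wallis and Dunn's pot hoc test) will be provided for all primary and secondary efficacy criteria". The sentence in full extends this to every visit, since these results "will be provided for all primary and secondary efficacy criteria at all points in time". The section also promises descriptive statistics and graphs for the ITT population.

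**The concern.** The objective is a question of association: do patients with worse cognition have different ET or qEEG values? The inferential tool offered answers another question: do the three treatment arms differ on the parameter? Neither answer implies the other. A parameter can follow cognition closely while the arms look alike, and arms can differ on a parameter that has nothing to do with cognition.

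At stake is one stated secondary objective. Followed exactly, the plan would produce ET and qEEG results by arm, and any statement about their value as biomarkers would have to come from an analysis chosen later.

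**Working it through.** The documents give no figure to reproduce here. The check is mainly a comparison of texts, followed by a feasibility calculation.

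**1. Is there an association analysis anywhere?** The SAP sections on endpoints (8), efficacy criteria (9), methodology (12) and analyses (13) contain no correlation, regression, classification analysis or cognitive reference score for ET or qEEG. Nor do protocol sections 9.2, 13.5, 13.6 and 13.11. The Mann-Whitney effect sizes in protocol section 13.11 are also two-group measures. The method that the protocol deferred does not appear in the SAP.

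**2. Does the Kruskal-Wallis sentence reach ET and qEEG?** It covers secondary efficacy criteria. SAP section 8.2 has three secondary endpoints: ET, qEEG and rTMS adverse events. The first two are the only ones that are not safety measures, so they are the natural referent. If they are not efficacy criteria, no inferential method applies to them.

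**3. Does a between-arm test carry the information?** A simulation of 3 arms of 30 patients (5,000 runs per setting, two-sided 0.05, all correlations assumed) shows the separation.

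| Assumed setting | Kruskal-Wallis by arm rejects | Spearman, parameter vs cognition, rejects |
|---|---|---|
| r = 0.3, no arm effect | 4.9% | 78% |
| r = 0.5, no arm effect | 5.2% | 99.8% |
| r = 0.9, no arm effect | 4.8% | 100% |
| r = 0, one arm shifted by 0.8 SD | 88% | 4.9% (shift removed) |

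The simulation builds in independence between arm and association, so it illustrates the logic and is not evidence about this trial.

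**4. Could the trial answer the question?** Protocol section 11.1 and SAP section 7 schedule ET, qEEG and all cognitive tests together at baseline, Day 101 and Day 180. SAP section 6.2 plans 3 × 30 = 90 patients. Precision of a Spearman correlation, with r = 0.4 as an assumption:

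- Fisher z = 0.5 × ln(1.4/0.6) = 0.424.
- SE = 1.03/√(90 − 3) = 0.110.
- Limits on the z scale: 0.424 ± 1.96 × 0.110 = 0.207 to 0.640.
- Back-transformed 95% CI: **0.20 to 0.56**.

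The same formula gives 0.09 to 0.48 for r = 0.3 and 0.32 to 0.64 for r = 0.5. With 10% loss (n = 81), SE = 1.03/√78 = 0.117, and the interval for r = 0.4 becomes about 0.19 to 0.57.

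**The case against.** The strongest reply is that the defect is an omission rather than a wrong choice of test. SAP section 9 lists nine scales as efficacy criteria, with neither ET nor qEEG among them. On a strict reading section 13.4 therefore does not touch them. That reading is possible, but it does not rescue the plan: the objective is then left with no inferential method at all. Both readings end in the same place.

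The reply also limits how far the point can be pressed. A reader might infer any of the following, and the documents do not support them:

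- *That a rank test is the only analysis of any kind.* SAP sections 12.2 and 13.4 also give descriptive statistics and graphs. The statistics listed are univariate and do not relate ET or qEEG to cognition, so the claim is limited to inferential methods.
- *That the absence of ET and qEEG from the coding list in SAP section 4 shows they will not be analysed.* That list is introduced as serving the primary efficacy analysis, so their absence is expected.
- *That the plan sets up a search across 32 channels and five recording sequences.* Protocol section 9.2 describes the recording. No document says every channel and sequence will be tested.

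It is also fair to say that the study is described as exploratory, and that Spearman is one reasonable choice among several, because neither document defines what would make a parameter a biomarker. Both points stand. They bear on how much weight the issue carries, not on whether the objective has an analysis.

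**Conclusion.** The concern holds in this form: the biomarker objective is stated in both documents, its method was deferred to the SAP, and the SAP contains no analysis that estimates whether any ET or qEEG parameter follows cognition. The finding rests on the text and needs no numerical assumption.

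The consequence is confined to one secondary objective. The primary comparison, its error rate and the safety analysis are untouched. This should be corrected, but it does not threaten the trial's main conclusion.

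The interval of 0.20 to 0.56 shows only that a useful estimate is within reach. It assumes r = 0.4, which no document gives, and complete ET, qEEG and cognitive data on all 90 patients. It does not measure harm from the present plan.

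**What to change.** In the SAP, before unblinding:

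1. Name a short list of ET and qEEG parameters and one principal cognitive reference score available at all three visits. The MoCA total is one candidate; the choice belongs to the trial team.
2. Estimate the Spearman correlation with 95% CI between each parameter and that score at baseline (pooled over arms), and at Day 101 and Day 180 (partial for arm). The two later visits match the 3- and 6-month timing in protocol section 13.5. Add change-to-change correlations as supportive.
3. State the number of correlations and label them exploratory. With five parameters (an assumption), one score and three visits there are 5 × 1 × 3 = 15, plus 5 × 2 = 10 for changes. Using all eight cognitive tests at three time points would give 5 × 8 × 3 = 120, which is why one principal score is preferable.
4. Reconcile protocol section 13.5 with SAP section 5.2 on the treatment-monitoring objective. If it is kept, add it to the SAP and use the arm comparison of ET and qEEG for that objective only.

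The cost is SAP wording and a small extra analysis. No new visits, assessments or patients are needed.
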